### 7. STUDY POPULATION

## 7.1. Description of population

The study population will include adults aged ≥50 YOA who are beneficiaries in the OptumTM database, diagnosed with an AID (defined as RA, IBD [UC or CD], SLE, PsO, PsA and MS), and who received RZV vaccination (along with their unvaccinated matches) anytime between 1 January 2018 to 31 December 2021 (Section 7.5 describes the algorithms for identification of AIDs). Co-existence of more than one AID can occur – while it is not required that each AID cohorts be mutually exclusive, overlap is expected to be minimal. Details of inclusion and exclusion criteria are defined in Sections 7.2 and 7.3.

Table 1 shows the demographic characteristics of beneficiaries in the OptumTM database diagnosed with RA, IBD, SLE, PsO, PsA and MS during the study period (2018-2021) based on the inclusion criteria (Section 7.2) and exclusion criteria (Section 7.3). Most of the beneficiaries with SLE (38.6%), PsA (38.9%), and MS (47.3%) were 50-59 YOA, while most of the participants with IBD (39.4%), RA (42.8%), and PsO (36.9%) were

219111 (EPI-ZOSTER-097 VE US DB)
Protocol Final

>70 YOA. Most of these beneficiaries were female while over 60% were white in all AID groups.

Table 1 Demographic characteristics of beneficiaries by AID condition\* during the study period (2018^-2021).

	SLE		IBD		RA		PsO		PsA		MS	
	N	%	N	%	N	%	N	%	N	%	N	%
Age at AID diagnosis (years)												
50-59												47.
	7740	38.6	11254	34.4	32130	30.5	22794	35.5	6194	38.9	10150	3
60-69												31.
	6086	30.4	8577	26.2	28028	26.6	17668	27.5	4968	31.2	6828	8
≥70												20.
	6224	31	12875	39.4	45029	42.8	23680	36.9	4747	29.8	4463	8
Sex												
Female												76.
	17665	88.1	18690	57.1	79127	75.2	34772	54.2	9314	58.5	16431	6
Male												23.
	2385	11.9	14016	42.9	26060	24.8	29370	45.8	6595	41.5	5010	4
Race /Ethnicity	1											
Asian	446	2.2	593	1.8	2331	2.2	1853	2.9	342	2.1	208	1
Black												10.
	3824	19.1	2796	8.5	13609	12.9	4440	6.9	930	5.8	2290	7
Hispanic	2492	12.4	2296	7	13491	12.8	5530	8.6	1505	9.5	1262	5.9
Multiple/Other/												
Unknown	1076	5.4	1529	4.7	5299	5	2944	4.6	760	4.8	972	4.5
White												77.
	12212	60.9	25492	77.9	70457	67	49375	77	12372	77.8	16709	9
Total	20050	-	32706	-	105187	-	64142	-	15909	-	21441	-

\*Table presents overall distribution of beneficiaries' characteristics by AID; no information on vaccination status (see Table 3).

## 7.2. Inclusion criteria

Participants will be included in the study if the following inclusion criteria are met:

- Age >50 YOA at the index date for all study objectives and registered as beneficiary in the OptumTM database.
- Meet criteria for RA, IBD, SLE, MS, PsO or PsA prior to the index date (Section 7.5).
- Receipt of first dose of RZV on or after 1 January 2018.
- 365 days of continuous enrollment (allowing administrative gaps 30 days) prior to the index date (baseline period) and continuous enrollment in the 30 days after the index date.
- At least 3 months of follow-up time.

<sup>^Beneficiaries in 2017 were included if they were vaccinated in early 2018. Random index dates for unvaccinated beneficiaries were defined; some AID diagnoses were selected in 2017.

219111 (EPI-ZOSTER-097 VE US DB)
Protocol Final

#### 7.3. Exclusion criteria

Participants will be excluded from the study if the following exclusion criteria are met:

- Any previous RZV doses before index date (for unvaccinated participants only) using all available data.
- Receipt of second dose of RZV less than 28 days apart since ACIP guidelines state that these participants must repeat the second dose [Dooling, 2018].
- Receipt of ZVL any time during the baseline as this may affect rates of HZ.
- HZ diagnosis or prescription fills for oral acyclovir, valacyclovir or famciclovir
  given specifically for HZ and within 30 days of index date since it is unclear if the
  HZ episode began before or after the index date and whether the length of time since
  vaccination (for RZV vaccinated participants) is long enough to allow for sufficient
  development of immunity.
- HZ diagnosis or prescription fills for oral acyclovir, valacyclovir or famciclovir in the 12 months before the index date to ensure that HZ diagnoses after the index date are new, rather than carried over from HZ episodes prior to the index date.
- Postherpetic neuralgia (PHN) diagnosis in the 12 months before the index date.
- Censoring events within 30 days after the index date (before the start of follow-up) (Section 7.7).
- Follow up time is less than 3 months after the follow up start date.

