Twelve matched cohorts for a 1-dose and 2-dose for each AID condition (SLE, MS, RA, IBD [ulcerative colitis (UC), Crohn's disease (CD)], PsO, and PsA) will be considered. Participants will be followed through OptumTM database from index date + 30 days until the earliest date of the occurrence of HZ, termination of continuous enrolment (period of uninterrupted insurance coverage), date of death (described in detail in the statistical analysis plan [SAP]), receipt of a dose of RZV for unvaccinated participants, receipt of RZV dose 2 for 1-dose cohort, receipt of zoster vaccine live (ZVL), or end of the study period (December 31, 2021). To be eligible for the analysis, participants who are >50 YOA at the index date will be required to have at least 365 days of continuous medical and pharmaceutical coverage (allowing administrative gap of 30 days) immediately before index date and 30 days after index date. The 365 days before the index date is defined as the baseline period. Following matching, propensity scores based on the likelihood of receiving RZV versus no RZV vaccination will be calculated using logistic regression models to balance measured confounders among participants receiving RZV and comparator participants with no prior RZV vaccination. The overall incidence rates of HZ for the 2-dose RZV vaccinated cohort and the matched unvaccinated cohort will be estimated. VE will be calculated from the hazard ratio obtained from Cox regression models. Analyses will be conducted separately in RA, IBD (UC, CD), SLE, MS, PsO, and PsA populations. Section 5 provides further study design details.

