# 3.1. Description of the database

This study will be conducted using data from the health care administrative encounters/claims (United enrollees) of the Clinformatics Data Mart (CDM) OptumTM. CDM OptumTM is a quarterly updated database for members of a large national managed care company affiliated with OptumTM. It includes both commercial and Medicare Advantage health plan enrollees from all 50 states in the United States. The database includes proprietary, deidentified health claims data from a geographically diverse US population (16% West, 20% Midwest, 36% South, and 27% Northeast). In addition to medical claims, pharmacy claims, and outpatient laboratory tests, OptumTM includes data tables related to member inpatient confinements and eligibility data. OptumTM includes

219111 (EPI-ZOSTER-097 VE US DB)
Protocol Final

data with service dates from 2007 to present and approximately 15 – 18 million annually insured lives. The OptumTM database system contains more than 80 million lives, of which more than 40% have more than 4 years of clinical history. Clinical history data are sourced from the electronic health record (EHR) of the large integrated delivery networks (IDNs), with more than 60% of patients having both outpatient and hospital information. Remaining patients come from large multispecialty physician practices. The age and sex distribution of the beneficiaries of OptumTM is similar to that reported by the US Census Bureau for the commercially insured and the Medicare managed care populations. This study will use IDN lives to provide information on healthcare use from both an inpatient and outpatient perspective.

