#### 6.2. Other variables

Other variables will be identified from the OptumTM database and considered in the analyses when appropriate as covariates. A list of covariates to be included followed by a detailed description of covariates and sources is in section 6.3.

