Presence of co-morbidities: kidney disease, cardiovascular disease, pulmonary disease [i.e., chronic obstructive pulmonary disease or chronic bronchitis, asthma], liver disease, diabetes mellitus, other autoimmune diseases, cancer, immunocompromising conditions [i.e., human immunodeficiency virus, cancer, transplant, immune-suppressive medications], SARS-CoV-2 infection/COVID-19 diagnosis with an index date after 2020) in the 365 days prior to the index date [Kawai, 2017a; Marra, 2020; Tsai, 2017; Yun, 2016].

Concomitant vaccinations during baseline: Influenza vaccine, tetanus, diphtheria and pertussis vaccine, pneumococcal vaccine in the 365 days prior to the index date, as a proxy for health behaviors.

Region of residence within U.S. as defined by the Census Bureau (4 regions: West, Midwest, South, Northeast) most recently prior to the index date [Izurieta, 2021; Sun, 2021].

Use of preventative services: screening, preventative visits in the 365 days prior to the index date [Izurieta, 2021].

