# 7.6. Matching

For the primary objectives, once sub-cohorts for each AID condition are identified, participants meeting inclusion criteria who receive 2 doses of RZV at least 28 days apart at the index date will be matched exactly with unvaccinated participants on age category by 5-year increments (50-54, 55-59, 60-64, 65-69, 70-74, 75-79, ≥80) and AID-related medication category (mutually exclusive) based on current use at the index date within the same AID group. Medication categories will be based on the medication windows described in 13.6. For the secondary objectives, participants meeting inclusion criteria who receive 1 dose of RZV at the index date will be matched with unvaccinated participants by 5-year increments (i.e., 50-54 age grouping) and by AID-related medication category (mutually exclusive) based on current use at the index date. Matching will be done with replacement.

Following matching as described above, propensity scores based on the likelihood of receiving RZV dose 2 versus no RZV vaccination will be calculated using logistic regression models with RZV vaccination as the dependent variable and independent variables as outlined in Section 6.2 to select the 3 unvaccinated participants which are the closest to each vaccinated participant, to reach a ratio of RZV vaccinated to RZV unvaccinated of 1:3. Propensity scores will be calculated within each cohort defined by AID to balance measured confounders (details to be provided in the SAP) among patients receiving RZV dose 2 and comparator patients with no prior RZV vaccination. A second cohort of patients will be created to compare patients receiving RZV dose 1 to patients with no prior vaccination, using the same approach to calculate propensity scores within each cohort defined by AID based on the likelihood of receiving RZV dose 1 versus no RZV vaccination. An unvaccinated patient may serve as a comparator for both the dose 1 and dose 2 cohorts, although separate index dates will be applied.

Covariate balance will be assessed before and after applying propensity scores using standardized mean differences, with standardized differences of 0.2 suggestive of important imbalance [Austin, 2009a; Austin, 2009b]. Any covariate demonstrating imbalance after weighting, suggesting residual confounding, will be included as an

219111 (EPI-ZOSTER-097 VE US DB)
Protocol Final

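### Live zoster vaccine (ZVL) given more than a year before index is neither excluded nor a matching or propensity variable, so it is only partly controlled by proxies and the balance check cannot show it

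*Protocol*

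**What the plan says.** All references are to the protocol.

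- **Exclusion (7.3).** The ZVL criterion is "Receipt of ZVL any time during the baseline as this may affect rates of HZ". Section 1.3 fixes the window: "The 365 days before the index date is defined as the baseline period".
- **Prior RZV (7.3).** The same list searches much further back for RZV: "Any previous RZV doses before index date (for unvaccinated participants only) using all available data".
- **Data held (3.1).** The database contains "data with service dates from 2007 to present".
- **Exact matching (7.6).** The variables are 5-year age category and "AID-related medication category (mutually exclusive) based on current use at the index date within the same AID group".
- **Propensity score (7.6).** It uses "logistic regression models with RZV vaccination as the dependent variable and independent variables as outlined in Section 6.2". Section 6.2 passes this on: "A list of covariates to be included followed by a detailed description of covariates and sources is in section 6.3".
- **Vaccination covariates (6.3).** The only ones listed are "Influenza vaccine, tetanus, diphtheria and pertussis vaccine, pneumococcal vaccine in the 365 days prior to the index date".
- **Elsewhere.** ZVL otherwise appears only as a censoring event during follow-up (1.3, 5.1, 7.7). Neither the limitations (5.2.1) nor the sensitivity analyses named in 11.3.5 mention ZVL given before baseline.

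**The concern.** The protocol treats ZVL as something that may change the rate of herpes zoster: it excludes recent recipients and censors anyone who receives it during follow-up. A person given ZVL 13 months or several years before index nevertheless enters either arm with no record of it in the analysis.

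People who accepted an earlier zoster vaccine are plausibly more likely to accept RZV. If so, and if some protection remains, earlier ZVL lowers zoster risk more in the RZV arm than among the comparators, and RZV is credited with part of it. Section 5.2.1 already says that use of other vaccinations will be captured to limit healthy-user bias, and a previous zoster vaccine is an obvious candidate for that list.

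**Working it through.** The protocol gives no figure for earlier ZVL, so there is none to reproduce. The check has three steps.

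**1. What the 365-day window can see.** Table 3, adding the six diseases within each year of dose 2:

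- 2018: 269 + 640 + 1761 + 1280 + 277 + 299 = 4,526
- 2019: 831 + 1700 + 4787 + 3372 + 772 + 877 = 12,339
- 2020: 935 + 1906 + 5113 + 3996 + 967 + 997 = 13,914
- 2021: 875 + 1619 + 4267 + 3468 + 839 + 948 = 12,016

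Entries in 2019-2021: 12,339 + 13,914 + 12,016 = 38,269. All years: 38,269 + 4,526 = 42,795. Share: 38,269 / 42,795 = 89.4%. These are cohort entries, since one person may be in several disease cohorts. The table's overall row adds to 42,755, which gives 89.5%.

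A dose 2 on 1 January 2019 has a window opening on 1 January 2018, and later doses open later. Matched comparators share the index date. For about 89% of entries the exclusion therefore cannot detect ZVL given before 2018. Section 3 dates RZV approval to October 2017, so for these entries all ZVL from before RZV approval is out of reach. Zoster vaccination was in use by then: Section 12 cites a 2008 advisory-committee recommendation on zoster prevention and a 2012 study of zoster vaccination in older patients with immune-mediated diseases.

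**2. What the balance check can see.** Section 7.6 uses a standardized difference of 0.2 as the sign of important imbalance. For a yes/no variable this is d = (p1 - p2) / sqrt{[p1(1 - p1) + p2(1 - p2)] / 2}. With assumed ZVL shares in the RZV and unvaccinated arms:

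- 20% vs 10%: 0.10 / sqrt(0.125) = 0.28
- 30% vs 15%: 0.15 / sqrt(0.16875) = 0.37

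Both exceed 0.2. Neither would be reported, because the check covers listed covariates only. The rule that moves unbalanced covariates into the Cox model would not be triggered either.

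**3. Possible size.** Let p_v and p_u be the shares with earlier ZVL among RZV recipients and the unvaccinated, and r the residual protection, acting equally in both arms. Then observed VE = 1 - HR x (1 - p_v r) / (1 - p_u r). The documents give none of p_v, p_u or r, so all are assumptions. At a true VE of 60% (HR 0.4):

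- p_v 30%, p_u 15%, r 30%: 1 - 0.4 x 0.910 / 0.955 = 61.9% (+1.9 points)
- p_v 40%, p_u 15%, r 40%: 1 - 0.4 x 0.84 / 0.94 = 64.3% (+4.3 points)
- p_v = p_u, any r: the ratio is 1 and there is no bias

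A wider set was run with r from 20% to 50%. Among the combinations with more ZVL in the RZV arm (20% or 30% vs 10%, and 40% vs 20%), observed VE was 51.0% to 55.6% at a true VE of 50% (the protocol's design value), and 68.7% to 71.6% at a true VE of 68% (the Medicare figure cited in Section 1.1). If RZV recipients had less earlier ZVL than comparators, the shift reverses: 10% vs 20% with r 50% gives 47.2% at a true VE of 50%.

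**The case against.** **The comparator is no prior RZV.** A reader might infer that the protocol promises a group without any zoster vaccine and fails to deliver it. It does not promise that. Section 5.1 defines unvaccinated as having had no RZV, and such a group may properly include earlier ZVL recipients. What stands is the possible imbalance between arms.

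**Earlier ZVL is not wholly uncontrolled.** Age is matched in 5-year bands. Influenza, tetanus/diphtheria/pertussis and pneumococcal vaccination, preventive services and ambulatory visits enter the propensity score. These are partial proxies, and Section 5.2.1 admits residual confounding in general terms. They reduce the concern but do not replace a variable that can be measured directly.

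**The stated ground is modest.** The protocol says ZVL may affect zoster rates, and says so of receipt during baseline. It does not assert an effect, and it is silent on ZVL given years earlier.

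**A downward bias is tempting to claim.** If ZVL protects only people without RZV, p_u 15% and r 30% give 1 - 0.4 / 0.955 = 58.1%. That is mainly a different estimand: with equal ZVL shares it is the correct marginal effect of RZV against no RZV. It should not be counted as confounding.

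**The shift is small beside sampling error.** For SLE, 2910 x 1.3 x 17.02/1000 x 0.4 gives about 26 vaccinated events, and an approximate 95% interval at VE 60% of 40% to 73% (1:3 matching, equal follow-up, ignoring re-used comparators). For RA, with about 139 events, it is about 52% to 66%. A 2-to-4-point shift lies inside both. This limits the severity, but a larger sample does not remove a systematic shift.

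**The RZV search is not a full parallel.** RZV is the exposure and is recent, so searching all data covers a few years at most. For ZVL the look-back would differ by person: only 365 days of enrolment is required, and Section 3.1 reports more than 4 years of clinical history for just over 40% of lives. A fixed window at least gives equal ascertainment. This is a fair reason to keep it for the exclusion, but not to leave recorded ZVL out of the covariates.

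**The SAP may add it.** Balancing and sensitivity details are left to the SAP, so the absence of a sensitivity analysis is not itself a fault. The exclusion window and the covariate list, however, are fixed in the protocol.

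**Conclusion.** The point holds in limited form. ZVL given more than a year before index is not directly controlled: it falls outside the exclusion window for both arms, it is absent from the matching and propensity variables, and an imbalance would not show in the planned diagnostics. For about 89% of two-dose entries the window misses everything before 2018.

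Inflation of roughly 2 to 4 points at a true VE of 60% depends on two unverified conditions: that RZV recipients more often had earlier ZVL, and that it still protects. The documents establish neither, and equal shares with equal protection give no bias. They do not support saying that VE is biased by a known amount, or that the comparison is invalid. They do support saying that a plausible, measurable confounder has been left out when the data to record it are partly in hand.

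**What to change.** - Keep the 365-day ZVL exclusion in Section 7.3.
- Search ZVL in all available data before index for both arms.
- Add any recorded prior ZVL (yes/no) to Section 6.3, the propensity model and the balance table, for both the 2-dose and 1-dose cohorts.
- If it remains unbalanced, adjust for it in the Cox model under the rule already in Section 7.6.
- Optionally, add a sensitivity analysis excluding everyone with recorded prior ZVL.

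The cost is one extra flag from data already held. Section 13.4.3 lists codes for RZV only, so ZVL codes have to be added; the existing exclusion and censoring rules need them anyway. The drawback is that look-back varies with enrolment history and ZVL given before database entry stays unseen. Look-back length should therefore be reported by arm, and the flag described as recorded ZVL, not as complete history.

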# 5.2 Limitations and strengths

#### 5.2.1 Limitations

Various limitations must be considered in a retrospective matched cohort study design, including confounding, bias, and misclassification.

1. Definition of the cohorts: Though the majority of the algorithms that will be used to identify participants with AIDs have demonstrated a good positive predictive value (PPV) (Section 7.5), some misclassification is expected using the validated AID-specific algorithms given the difficulty in diagnosing some AIDs (e.g., SLE, MS). In addition, some participants with well controlled AIDs may not be captured, with algorithms biasing towards a higher risk group. To improve confidence in the definitions, similar algorithms that are being used in studies that are targeting AID

219111 (EPI-ZOSTER-097 VE US DB)
Protocol Final

populations [EPI-ZOSTER-041; EPI-ZOSTER-044] will be used. These studies rely on specialists (e.g., neurologists, rheumatologists, dermatologists) consultation to provide expert opinion on the definitions of the AIDs.

- 2. Outcome misclassification: Some participants that are reported as having a HZ occurrence may not have an accurate diagnosis of HZ occurrence, which may result in a possible underestimation of VE. However, this is expected to be minimal as the detection of HZ using an ICD-10 diagnosis code for HZ (B02.xx) from hospital, emergency department, or ambulatory visit diagnoses, and dispensing for an oral antiviral (acyclovir, valacyclovir, or famciclovir) within 7 days before or after the HZ diagnosis has been used to evaluate the HZ occurrence based on the available literature [Izurieta, 2021]. Systematic differences in HZ misclassification between vaccinated and unvaccinated are not expected.
- 3. Exposure misclassification: It is possible that some participants who are reportedly unvaccinated may have received RZV prior to entering the dataset, leading to an underestimation of VE. Receipt of RZV dose 1 or 2 will be identified from administrative and claims data by means of Current Procedural Terminology (CPT) code 90750 and National Drug Code (NDC) codes 58160-828-01, 58160-829-01, 58160-819-12, 58160-828-03, 58160-829-03, and 58160-823-11 to minimize the risk of exposure misclassification. Additional codes for identification of RZV vaccination may be considered if relevant codes become available in the future.

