# 7.7. Follow-up/censoring

The follow-up period will begin from 30 days after the index date (to allow development of immunity after vaccination) and will end at the earliest occurrence of the following events:

- HZ occurrence
- End of continuous enrolment (period of uninterrupted insurance coverage with gap allowance of 30 days).
- Death (date of death including the year and month of death).
- End of data availability/study period (December 31, 2021).
- Receipt of RZV (additional dose for vaccinated participants or first RZV dose in the case of unvaccinated participants):
  - For 2-dose VE, vaccinated participants will be censored upon receipt of a dose 3.
  - For 1-dose VE, vaccinated participants will be censored upon receipt of dose 2.
- Receipt of ZVL vaccination.

The latest date a patient can be enrolled to ensure minimum duration of follow up is 30 September 2021 to allow for at least 3 months follow-up to observe HZ.

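### HZ or PHN more than 12 months before index is neither screened out nor listed as a propensity covariate, so the plan does not directly balance it between arms

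*Protocol*

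**What the plan says.** **Exclusions.** Section 7.3 removes anyone with an HZ diagnosis or a fill of acyclovir, valacyclovir or "famciclovir in the 12 months before the index date to ensure that HZ diagnoses after the index date are new". The sentence goes on to say that the aim is to keep out events carried over from earlier episodes. A further criterion is "Postherpetic neuralgia (PHN) diagnosis in the 12 months before the index date". HZ diagnoses or antiviral fills "given specifically for HZ and within 30 days of index date" also exclude, as do censoring events in the 30 days after index. Section 7.7 adds that "The follow-up period will begin from 30 days after the index date".

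**Look-back for another variable.** For prior vaccination the same list goes further: "Any previous RZV doses before index date (for unvaccinated participants only) using all available data". Section 3.1 says that the database holds "data with service dates from 2007 to present".

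**Balancing.** Section 7.6 matches exactly on 5-year age band and AID medication category, then selects comparators by a propensity score built on the variables of Section 6.2. That section points to Section 6.3 for the list of covariates to be included. Section 6.3 covers demographics, medications, encounters, cost, co-morbidities, vaccinations, region and preventive services. It contains no item for HZ or PHN history. The limitations in Section 5.2.1 do not mention it either.

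**Outcome.** Section 4.3 requires one inpatient HZ claim, or two outpatient HZ claims at most 30 days apart, or one outpatient claim with an antiviral claim within 7 days. Section 13.4.2 gives the code as B02.xx.

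**The concern.** A person with HZ or PHN 13 or more months before index can enter either arm. Having had shingles is a plausible reason to seek the vaccine. It may also change the later chance of an HZ claim, upwards through recurrence or continuing care, or downwards. A variable linked to both exposure and outcome is a confounder, and a propensity score does not directly balance a variable left out of it.

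The plan's safeguard does not reach this gap. Section 7.6 adds a covariate to the Cox model when it shows imbalance after the propensity step, but only measured covariates are checked. An imbalance in older HZ history would go unseen.

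At stake is the adjusted HR, and so the VE, in the six primary 2-dose comparisons. The 1-dose comparisons use the same approach.

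**Working it through.** **1. Plan figures used for scale.** No figure in the protocol concerns past HZ. The Table 2 rates reproduce as cases divided by person-years: RA 2781/179079 = 15.53, PsA 499/34023 = 14.67, PsO 1533/134443 = 11.40 and SLE 565/33195 = 17.02 per 1000.

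**2. How common might past HZ be?** With 1 − exp(−rate × years), five person-years at 11.40 to 17.02 per 1000 give 5.5% to 8.2%, and ten years give about 11% to 16%. Past HZ is therefore not rare. This says nothing about a difference between arms.

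**3. Confounding.** For prevalence p_v in the vaccinated, p_u in the unvaccinated, and rate ratio RR for past HZ, the HR is multiplied by

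(1 + p_v(RR − 1)) / (1 + p_u(RR − 1)).

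All three inputs are assumptions.

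| Past HZ, vaccinated vs unvaccinated | RR 1.5 | RR 2 | RR 3 |
|---|---|---|---|
| 10% vs 8% | 1.010 | 1.019 | 1.034 |
| 15% vs 10% | 1.024 | 1.045 | 1.083 |
| 20% vs 10% | 1.048 | 1.091 | 1.167 |

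- Six of the nine cells lie below 1.05.
- A true VE of 50% (HR 0.50, the value used for the power claim in Section 11.1) reads 1 − 0.50 × 1.010 = 49.5% at the low end and 1 − 0.50 × 1.167 = 41.7% at the high end.
- A true VE of 68% (HR 0.32, the 2-dose estimate cited in Section 1.1) reads 67.7% to 62.7%.
- Equal prevalence gives a factor of 1.
- Reversal: RR 0.5 with 10% vs 5% gives 0.95/0.975 = 0.974, and a VE of 50% reads 51.3%. RR 3 with the arms swapped, 10% vs 20%, gives 1.20/1.40 = 0.857, and a VE of 50% reads 57.1%.

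**4. Comparison with random error.** Assume VE 50%, equal follow-up and distinct comparators at 1:3.

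- RA: 15,928 × 1.4 × 15.53/1000 × 0.5 ≈ 173 vaccinated events and 3 × 15,928 × 1.4 × 15.53/1000 ≈ 1,039 comparator events. The 95% CI factor is exp(1.96 × √(1/173 + 1/1039)) ≈ 1.17.
- PsA: 2,845 × 1.3 × 14.67/1000 × 0.5 ≈ 27 and 3 × 2,845 × 1.3 × 14.67/1000 ≈ 163 events. The factor is exp(1.96 × √(1/27 + 1/163)) ≈ 1.50.

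The extreme cell equals the random error in RA. It is well inside the random error in PsA.

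**5. Carry-over of old episodes.** To be miscounted, a person must have no HZ diagnosis, no PHN diagnosis and no oral antiviral fill for 12 months before index, and no HZ in the next 30 days. That is about 13 months of silence. The person must then meet the full Section 4.3 pattern. If such false events occur at the same absolute rate in both arms, equal to a fraction c of the true unvaccinated rate, the observed HR is (HR + c)/(1 + c). For assumed c of 1% to 10%, a true VE of 70% reads 69.3% to 63.6%, and 50% reads 49.5% to 45.5%. This is dilution towards zero effect, not inflation.

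**The case against.** The strongest reply is that a uniform 12-month window is a sound exclusion. Section 7.2 guarantees only 365 days of enrolment. Section 3.1 says only that more than 40% of lives in the database have over four years of history. A variable drawn from all data would be recorded unevenly and could itself be misclassified differently by arm. The contrast with prior RZV is also weak, because that search defines who counts as unvaccinated and the vaccine was approved only in October 2017. Propensity details are deferred to the SAP, and Section 5.2.1 concedes residual confounding. Past HZ may be partly balanced through age, medication, co-morbidity and use of care, and the most recent episodes are already excluded.

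Much of this stands. It justifies keeping the exclusion, and it means that the new covariate needs a safeguard for unequal look-back. It does not remove the gap, because Section 6.2 presents Section 6.3 as the list to be included and older HZ history is not on it.

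A reader might also infer that sequela visits from old episodes will be counted as new HZ because the outcome takes all of B02.xx. The documents do not show this. They do not list the sub-codes, Section 13.4.2 allows the codes to be updated, and step 5 shows how narrow the route is. A recurrence after a clean year is a new HZ event and a legitimate outcome.

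**Conclusion.** The gap is real and modest. HZ or PHN more than 12 months before index is neither excluded nor directly balanced, and the plan's imbalance check cannot detect it.

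The documents fix neither the size nor the direction of any bias. Under the assumed inputs the HR shifts by about 1% to 17%, mostly under 5%. The 17% requires both a doubled prevalence in the vaccinated and a threefold rate. If past HZ is more common in vaccinees and raises risk, VE is understated. If either assumption reverses, VE is overstated.

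A reader might conclude that VE is biased in all six primary cohorts. That would need an imbalance between arms for which the documents give no evidence. Carry-over is a secondary matter, and where it is similar in both arms it lowers VE. The point is a worthwhile, inexpensive improvement and does not invalidate the design.

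**What to change.** 1. Keep the 12-month exclusion in Section 7.3.
2. Add to Section 6.3: *any HZ or PHN diagnosis more than 12 months before the index date, using all available data (yes/no)*. Enter it in the propensity model and in the standardized-difference check of Section 7.6.
3. Because look-back length differs between people, also include length of prior enrolment as a covariate, or repeat the analysis with a fixed longer look-back in those who have it.
4. As a secondary check, add a sensitivity analysis that does not count events supported only by PHN codes.

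**Cost.** One or two derived variables from claims already held and one or two extra runs per cohort, with no change to the sample size. Uneven look-back leaves some past HZ unrecorded, a fixed longer look-back shrinks the cohort, and the PHN check may drop a few true episodes first coded as PHN.
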